10.3.2. Definition of SAE

If an event is not an AE per definition above, then it cannot be an SAE even if serious conditions are met (eg, hospitalization for signs/symptoms of the disease under study, death due to progression of disease).

A SAE is defined as any untoward medical occurrence that, at any dose:

a. Results in death

b. Is life-threatening

The term 'life-threatening' in the definition of 'serious' refers to an event in which the participant was at risk of death at the time of the event. It does not refer to an event, which hypothetically might have caused death, if it were more severe.

c. Requires inpatient hospitalization or prolongation of existing hospitalization

In general, hospitalization signifies that the participant has been detained (usually involving at least an overnight stay) at the hospital or emergency ward for observation and/or intervention that would not have been appropriate in the physician's office or outpatient setting. Complications that occur during hospitalization are AE. If a complication prolongs hospitalization or fulfills any other serious criteria, the event is serious. When in doubt as to whether "hospitalization" occurred or was necessary, the AE should be considered serious.

Hospitalization for elective intervention of a pre-existing condition that did not worsen from baseline is not considered an AE.

d. Results in persistent disability/incapacity

The term disability means a substantial disruption of a person's ability to conduct normal life functions.

This definition is not intended to include experiences of relatively minor medical significance such as uncomplicated headache, nausea, vomiting, diarrhea, influenza, and accidental trauma (eg, sprained ankle) which may interfere with or prevent everyday life functions but do not constitute a substantial disruption.

e. Is a congenital anomaly/birth defect**f. Other situations:**

Medical or scientific judgment should be exercised in deciding whether SAE reporting is appropriate in other situations such as important medical events that may not be immediately life-threatening or result in death or hospitalization but may jeopardize the participant or may require medical or surgical intervention to prevent one of the other outcomes listed in the above definition. These events should usually be considered serious.

Examples of such events include invasive or malignant cancers, intensive intervention in an emergency room or at home for allergic bronchospasm, blood dyscrasias or convulsions that do not result in hospitalization, or development of drug dependency or drug abuse.

10.3.3. Definition of Cardiovascular Events**Cardiovascular Events (CV) Definition:**

Investigators will be required to fill out the specific CV Event page of the CRF for the following AEs and SAEs:

Myocardial infarction/unstable angina

Congestive heart failure

Arrhythmias

Valvulopathy

Pulmonary hypertension

Cerebrovascular events/stroke and transient ischemic attack

Peripheral arterial thromboembolism

Deep venous thrombosis/pulmonary embolism

- Revascularization

10.3.4. Recording AE and SAE**AE and SAE Recording**

When an AE/SAE occurs, it is the responsibility of the investigator to review all documentation (eg, hospital progress notes, laboratory, and diagnostics reports) related to the event.

The investigator will then record all relevant AE/SAE information in the CRF.

It is **not** acceptable for the investigator to send photocopies of the participant's medical records to GSK in lieu of completion of the GSK /AE/SAE CRF page.

There may be instances when copies of medical records for certain cases are requested by GSK. In this case, all participant identifiers, with the exception of the participant number, will be redacted on the copies of the medical records before submission to GSK.

The investigator will attempt to establish a diagnosis of the event based on signs, symptoms, and/or other clinical information. Whenever possible, the diagnosis (not the individual signs/symptoms) will be documented as the AE/SAE.

Assessment of Intensity

The investigator will make an assessment of intensity for each AE and SAE reported during the study and assign it to one of the following categories:

Mild: An event that is easily tolerated by the participant, causing minimal discomfort and not interfering with everyday activities.

Moderate: An event that causes sufficiently discomfort and interferes with normal everyday activities.

Severe: An event that prevents normal everyday activities. An AE that is assessed as severe should not be confused with an SAE. Severe is a category utilized for rating the intensity of an event; and both AE and SAE can be assessed as severe.

An event is defined as 'serious' when it meets at least one of the predefined outcomes as described in the definition of an SAE, NOT when it is rated as severe.

Assessment of Causality

The investigator is obligated to assess the relationship between study intervention and each occurrence of each AE/SAE.

A "reasonable possibility" of a relationship conveys that there are facts, evidence, and/or arguments to suggest a causal relationship, rather than a relationship cannot be ruled out.

The investigator will use clinical judgment to determine the relationship.

Alternative causes, such as underlying disease(s), concomitant therapy, and other risk factors, as well as the temporal relationship of the event to study intervention administration will be considered and investigated.

The investigator will also consult the Investigator's Brochure (IB) and/or Product Information, for marketed products, in his/her assessment.

For each AE/SAE, the investigator **must** document in the medical notes that he/she has reviewed the AE/SAE and has provided an assessment of causality.

There may be situations in which an SAE has occurred and the investigator has minimal information to include in the initial report to GSK. However, **it is very important that the investigator always make an assessment of causality for every event before the initial transmission of the SAE data to GSK.**

The investigator may change his/her opinion of causality in light of follow-up information and send an SAE follow-up report with the updated causality assessment.

The causality assessment is one of the criteria used when determining regulatory reporting requirements.

Follow-up of AE and SAE

The investigator is obligated to perform or arrange for the conduct of supplemental measurements and/or evaluations as medically indicated or as requested by GSK to elucidate the nature and/or causality of the AE or SAE as fully as possible. This may include additional laboratory tests or investigations, histopathological examinations, or consultation with other health care professionals.

If a participant dies during participation in the study or during a recognized follow-up period, the investigator may be asked to provide GSK with a copy of any post-mortem findings including histopathology.

New or updated information will be recorded in the originally completed CRF.

The investigator will submit any updated SAE data to GSK within 24 hours of receipt of the information.

10.3.5. Reporting of SAE to GSK

SAE Reporting to GSK via Electronic Data Collection Tool

The primary mechanism for reporting SAE to GSK will be the electronic data collection tool.

If the electronic system is unavailable, then the site will use the paper SAE data collection tool as outlined in the SRM in order to report the event within 24 hours. The site will enter the SAE data into the electronic system as soon as it becomes available.

The investigator or medically-qualified sub-investigator must show evidence within the eCRF (e.g., check review box, signature, etc.) of review and verification of the relationship of each SAE to IP/study participation (causality) within 72 hours of SAE entry into the eCRF.

After the study is completed at a given site, the electronic data collection tool will be taken off-line to prevent the entry of new data or changes to existing data.

If a site receives a report of a new SAE from a study participant or receives updated data on a previously reported SAE after the electronic data collection tool has been taken off-line, then the site can report this information to the medical monitor by telephone.

Contacts for SAE reporting can be found in the SRM.

SAE Reporting to GSK via Paper CRF

- Facsimile transmission of the SAE paper CRF is the preferred method to transmit this information to the **medical monitor**
- In rare circumstances and in the absence of facsimile equipment, notification by telephone is acceptable with a copy of the SAE data collection tool sent by overnight mail or courier service.
- Initial notification via telephone does not replace the need for the investigator to complete and sign the SAE CRF pages within the designated reporting time frames.
- Contacts for SAE reporting can be found in SRM.

10.4. Appendix 4: Contraceptive Guidance and Collection of Pregnancy Information

10.4.1. Definitions

Woman of Childbearing Potential (WOCBP)

A woman is considered fertile following menarche and until becoming post-menopausal unless permanently sterile (see below)

Women in the following categories are not considered WOCBP

1. Premenarchal
2. Premenopausal female with ONE of the following:

- Documented hysterectomy
- Documented bilateral salpingectomy
- Documented bilateral oophorectomy

Note: Documentation can come from the site personnel's: review of participant's medical records, medical examination, or medical history interview.

3. Postmenopausal female

- A postmenopausal state is defined as no menses for 12 months without an alternative medical cause. A high follicle stimulating hormone (FSH) level in the postmenopausal range may be used to confirm a postmenopausal state in women not using hormonal contraception or hormonal replacement therapy (HRT). However, in the absence of 12 months of amenorrhea, a single FSH measurement is insufficient.
- Females on HRT and whose menopausal status is in doubt will be required to use one of the non-hormonal highly effective contraception methods if they wish to continue their HRT during the study. Otherwise, they must discontinue HRT to allow confirmation of postmenopausal status before study enrolment.

10.4.2. Contraception Guidance

Male participants

Male participants with female partners of childbearing potential are eligible to participate if they agree to ONE of the following while on study intervention and for 100 days after the last dose

- Are abstinent from penile-vaginal intercourse as their usual and preferred lifestyle (abstinent on a long-term and persistent basis) and agree to remain abstinent.
- Agree to use a male condom plus an additional method of contraception with a failure rate of <1% per year as described below when having penile-vaginal intercourse with a woman of childbearing potential.

Men with a pregnant or breastfeeding partner must agree to remain abstinent from penile-vaginal intercourse or use a male condom during each episode of penile penetration while on study intervention and for 100 days after the last dose

- In addition male participants must refrain from donating sperm for duration of study and for 100 days after last dose.

Female participants

Female participants of childbearing potential are eligible to participate if they agree to use a highly effective method of contraception consistently and correctly as described in the Table below.

Highly Effective Contraceptive Methods

CONTRACEPTIVES^a ALLOWED DURING THE STUDY INCLUDE:
Highly Effective Methods^b That Have Low User Dependency
Implantable progestogen-only hormone contraception associated with inhibition of ovulation ^c
Intrauterine device (IUD)
Intrauterine hormone-releasing system (IUS) ^c
Bilateral tubal occlusion
Vasectomized partner Note: Vasectomized partner is a highly effective contraceptive method provided that the partner is the sole sexual partner of the woman of childbearing potential and the absence of sperm has been confirmed. If not, an additional highly effective method of contraception should be used. Spermatogenesis cycle is approximately 90 days.
Highly Effective Methods^b That Are User Dependent
Combined (estrogen- and progestogen-containing) hormonal contraception associated with inhibition of ovulation ^c oral intravaginal transdermal injectable
Progestogen-only hormone contraception associated with inhibition of ovulation ^c oral injectable
Sexual abstinence Note: Sexual abstinence is considered a highly effective method only if defined as refraining from heterosexual intercourse during the entire period of risk associated with the study intervention. The reliability of sexual abstinence needs to be evaluated in relation to the duration of the study and the preferred and usual lifestyle of the participant

Contraceptive use by men or women should be consistent with local regulations regarding the use of contraceptive methods for those participating in clinical studies.

Failure rate of <1% per year when used consistently and correctly. Typical use failure rates differ from those when used consistently and correctly.

Note: Periodic abstinence (calendar, sympto-thermal, post-ovulation methods), withdrawal (coitus interruptus), spermicides only, and lactational amenorrhoea method (LAM) are not acceptable methods of contraception for this study. Male condom and female condom should not be used together (due to risk of failure with friction)

Pregnancy Testing

WOCBP should only be included after a confirmed menstrual period and a negative highly sensitive serum pregnancy test

Additional pregnancy testing should be performed at monthly intervals during the intervention period and at 150 days after the last dose of study intervention and as required locally.

Pregnancy testing will be performed whenever a menstrual cycle is missed or when pregnancy is otherwise suspected.

10.4.3. Collection of Pregnancy Information

Male participants with partners who become pregnant

Investigator will attempt to collect pregnancy information on any male participant's female partner of a male study participant who becomes pregnant while participating in this study. This applies only to participants who receive study intervention.

After obtaining the necessary signed informed consent from the pregnant female partner directly, the investigator will record pregnancy information on the appropriate form and submit it to GSK within 24 hours of learning of the partner's pregnancy.

Partner will also be followed to determine the outcome of the pregnancy. Information on the status of the mother and child will be forwarded to GSK

Generally, follow-up will be no longer than 6 to 8 weeks following the estimated delivery date. Any termination of the pregnancy will be reported regardless of fetal status (presence or absence of anomalies) or indication for procedure.

Female Participants who become pregnant

Investigator will collect pregnancy information on any female participant, who becomes pregnant while participating in this study.

Information will be recorded on the appropriate form and submitted to GSK within 24 hours of learning of a participant's pregnancy.

Participant will be followed to determine the outcome of the pregnancy. The investigator will collect follow-up information on participant and neonate, which will be forwarded to GSK. Generally, follow-up will not be required for longer than 6 to 8 weeks beyond the estimated delivery date.

Any termination of pregnancy will be reported, regardless of fetal status (presence or absence of anomalies) or indication for procedure.

While pregnancy itself is not considered to be an AE or SAE, any pregnancy complication or elective termination of a pregnancy will be reported as an AE or SAE.

A spontaneous abortion is always considered to be an SAE and will be reported as such.

Any SAE occurring as a result of a post-study pregnancy which is considered reasonably related to the study intervention by the investigator, will be reported to GSK as described in [Appendix 3](#). While the investigator is not obligated to actively seek this information in former study participants, he or she may learn of an SAE through spontaneous reporting.

Any female participant who becomes pregnant while participating will discontinue study intervention

10.5. Appendix 5: Genetics

USE/ANALYSIS OF DNA

Genetic variation may impact a participant's response to therapy, susceptibility, severity and progression of disease. Variable response to therapy may be due to genetic determinants that impact drug absorption, distribution, metabolism, and excretion; mechanism of action of the drug; disease etiology; and/or molecular subtype of the disease being treated. Therefore, where local regulations and IRB/IEC allow, a blood sample will be collected for DNA analysis

DNA samples will be used for research related to GSK3368715 or advanced solid tumors or DLBCL and related diseases. They may also be used to develop tests/assays including diagnostic tests related to GSK3368715 or study interventions of this drug class, and advanced solid tumors or DLBCL Genetic research may consist of the analysis of one or more candidate genes or the analysis of genetic markers throughout the genome [or analysis of the entire genome] (as appropriate)

DNA samples will be analyzed if it is hypothesized that this may help further understand the clinical data.

DNA samples will be analyzed by using appropriate descriptive and/or statistical analysis methods. A detailed description of any planned analyses will be documented in a RAP prior to initiation of the analysis. The samples may be analyzed as part of a multi-study assessment of genetic factors involved in the response to GSK3368715 or study interventions of this class. The results of genetic analyses may be reported in the CSR or in a separate study summary.

The sponsor will store the DNA samples in a secure storage space with adequate measures to protect confidentiality.

The samples will be retained while research on GSK3368715 (or study interventions of this class) or advanced solid tumors or DLBCL continues but no longer than 15 years after the last participant last visit or other period as per local requirements.

10.6. Appendix 6: Liver Safety: Required Actions and Follow-up Assessments and Study intervention Rechallenge Guidelines

Phase I liver chemistry stopping and increased monitoring criteria have been designed to assure participant safety and evaluate liver event etiology (in alignment with the FDA premarketing clinical liver safety guidance).

<http://www.fda.gov/downloads/Drugs/GuidanceComplianceRegulatoryInformation/Guidances/UCM174090.pdf>.

Phase I liver chemistry stopping criteria and required follow up assessments

Liver Chemistry Stopping Criteria – Liver Stopping Event Participant with entry criteria ALT ≤ 2.5 x ULN	
ALT-absolute	ALT ≥ 5xULN
ALT Increase	ALT ≥ 3xULN persists for ≥4 weeks
Bilirubin^{1,2}	ALT ≥ 3xULN and bilirubin ≥ 2xULN (>35% direct bilirubin)
INR²	ALT ≥ 3xULN and INR>1.5, if INR measured
Cannot Monitor	ALT ≥ 3xULN and cannot be monitored weekly for 4 weeks
Symptomatic³	ALT ≥ 3xULN associated with symptoms (new or worsening) believed to be related to liver injury or hypersensitivity
Liver Chemistry Stopping Criteria – Liver Stopping Event Including participants with documented liver metastases/tumor infiltration at baseline AND entry criteria ALT >2.5 x ULN but ≤ 5 x ULN	
ALT-absolute	Both ALT ≥ 5xULN and ≥2x baseline value
ALT Increase	Both ALT ≥ 3xULN and ≥ 1.5x baseline value that persists for ≥4 weeks
Bilirubin^{1,2}	ALT ≥ 3xULN and bilirubin ≥ 2xULN (>35% direct bilirubin)
INR²	ALT ≥ 3xULN and INR>1.5, if INR measured
Cannot Monitor	Both ALT ≥ 3xULN and ≥ 1.5x baseline value that cannot be monitored for 4 weeks
Symptomatic³	Both ALT ≥ 3xULN and ≥ 1.5x baseline value associated with symptoms (new or worsening) believed to be related to liver injury or hypersensitivity

Required Actions and Follow up Assessments following ANY Liver Stopping Event	
Actions	Follow Up Assessments

 • Immediately discontinue study intervention • Report the event to GSK within 24 hours • Complete the liver event CRF and complete an SAE data collection tool if the event also meets the criteria for an SAE² • Perform liver event follow up assessments • Monitor the participant until liver chemistries resolve, stabilize, or return to within baseline (see MONITORING below) • Do not restart/rechallenge participant with study intervention unless allowed per protocol and GSK Medical Governance approval is granted (refer to Appendix 6) • If restart/rechallenge not allowed per protocol or not granted, permanently discontinue study intervention and may continue participant in the study for any protocol specified follow up assessments 
MONITORING:
 
For bilirubin or INR criteria:
 
 • Repeat liver chemistries (include ALT, AST, alkaline phosphatase, bilirubin) and perform liver event follow up assessments within 24 hrs • Monitor participants twice weekly until liver chemistries resolve, stabilize or return to within baseline • A specialist or hepatology consultation is recommended 
For All other criteria:
 
 • Repeat liver chemistries (include ALT, AST, alkaline phosphatase, bilirubin) and perform liver event follow up assessments within 24-96 hrs • Monitor participants weekly until liver chemistries resolve, stabilize or return to within baseline 	
 • Viral hepatitis serology⁴ • Only in those with underlying chronic hepatitis B at study entry (identified by positive hepatitis B surface antigen) quantitative hepatitis B DNA and hepatitis delta antibody⁵. • Blood sample for pharmacokinetic (PK) analysis, obtained 24-72h after last dose⁶ • Serum creatine phosphokinase (CPK) and lactate dehydrogenase (LDH). • Fractionate bilirubin, if total bilirubin $\geq 2 \times \text{ULN}$ • Obtain complete blood count with differential to assess eosinophilia • Record the appearance or worsening of clinical symptoms of liver injury, or hypersensitivity, on the AE report form • Record use of concomitant medications on the concomitant medications report form including acetaminophen, herbal remedies, other over the counter medications • Record alcohol use on the liver event alcohol intake case report form 
For bilirubin or INR criteria:
 
 • Anti-nuclear antibody, anti-smooth muscle antibody, Type 1 anti-liver kidney microsomal antibodies, and quantitative total immunoglobulin G (IgG or gamma globulins). • Serum acetaminophen adduct HPLC assay (quantifies potential acetaminophen contribution to liver injury in participants with definite or likely acetaminophen use in the preceding week [James, 2009]). NOTE: not required in China • Liver imaging (ultrasound, magnetic resonance, or computerised tomography) and /or liver biopsy to evaluate liver disease: complete Liver Imaging and/or Liver Biopsy CRF forms.

1. Serum bilirubin fractionation should be performed if testing is available. If serum bilirubin fractionation is not immediately available, discontinue study intervention for that participant if ALT \geq 3xULN **and** bilirubin \geq 2xULN. Additionally, if serum bilirubin fractionation testing is unavailable, **record presence of detectable urinary bilirubin on dipstick**, indicating direct bilirubin elevations and suggesting liver injury.
2. All events of ALT \geq 3xULN **and** bilirubin \geq 2xULN (>35% direct bilirubin) or ALT \geq 3xULN **and** INR>1.5, if INR measured which may indicate severe liver injury (possible 'Hy's Law'), **must be reported as an SAE (excluding studies of hepatic impairment or cirrhosis)**; INR measurement is not required and the threshold value stated will not apply to participants receiving anticoagulants
3. New or worsening symptoms believed to be related to liver injury (such as fatigue, nausea, vomiting, right upper quadrant pain or tenderness, or jaundice) or believed to be related to hypersensitivity (such as fever, rash or eosinophilia)
4. Includes: Hepatitis A IgM antibody; Hepatitis B surface antigen and Hepatitis B Core Antibody (IgM); Hepatitis C RNA; Cytomegalovirus IgM antibody; Epstein-Barr viral capsid antigen IgM antibody (or if unavailable, obtain heterophile antibody or monospot testing); Hepatitis E IgM antibody
5. If hepatitis delta antibody assay cannot be performed, it can be replaced with a PCR of hepatitis D RNA virus (where needed) [Le Gal, 2005](#)].
6. PK sample may not be required for participants known to be receiving placebo or non-GSK comparator interventions.) Record the date/time of the PK blood sample draw and the date/time of the last dose of study intervention prior to blood sample draw on the CRF. If the date or time of the last dose is unclear, provide the participant's best approximation. If the date/time of the last dose cannot be approximated OR a PK sample cannot be collected in the time period indicated above, do not obtain a PK sample. Instructions for sample handling and shipping are in the SRM.

Phase I Oncology liver chemistry increased monitoring criteria with continued therapy

Liver Chemistry Increased Monitoring Criteria – Liver Monitoring Event	
Criteria	Actions

Participant with entry criteria ALT\leq2.5x ULN ALT \geq3xULN but $<$5xULN and bilirubin $<$2xULN, without symptoms believed to be related to liver injury or hypersensitivity and who can be monitored weekly for 4 weeks
 
Participant with documented liver metastases/tumor infiltration at baseline AND entry criteria ALT$>$2.5 x ULN but \leq 5 x ULN ALT \geq3x ULN and 1.5x baseline value but ALT $<$5x ULN and 2x baseline value and bilirubin $<$2xULN, without symptoms believed to be related to liver injury, or hypersensitivity and who can be monitored weekly for 4 weeks
	
 • Notify the GSK medical monitor within 24 hours of learning of the abnormality to discuss participant safety. • Participant can continue study intervention • Participant must return weekly for repeat liver chemistries (ALT, AST, alkaline phosphatase, bilirubin) until they resolve, stabilise or return to within baseline • If at any time participant meets the liver chemistry stopping criteria, proceed as described above 
For participants with entry criteria ALT\leq2.5 x ULN
 
 • If, after 4 weeks of monitoring, ALT $<$3xULN and bilirubin $<$2xULN, monitor participants twice monthly until liver chemistries normalize or return to within baseline. 
For participants with documented liver metastases/tumor infiltration at baseline AND entry criteria ALT$>$2.5 x ULN but \leq 5 x ULN
 
 • If, after 4 weeks of monitoring, ALT $<$3xULN and $<$1.5x baseline value, and bilirubin $<$2xULN, monitor participants twice monthly until liver chemistries normalize or return to within baseline

References

10.7. Appendix 7: Medical Device Incidents: Definition and Procedures for Recording, Evaluating, Follow-up, and Reporting

There are no medical devices used in this protocol.

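### Appendix 6, entry ALT up to 2.5×ULN: ALT 3 to <5×ULN with bilirubin ≥2×ULN and a known direct fraction ≤35% meets neither the stopping nor the monitoring criteria, so the 24-hour notification is not triggered

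*Protocol*

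**What the plan says.** All of the following is in Protocol Section 10.6 (Appendix 6), for participants with entry ALT ≤2.5×ULN.

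- **Stopping table, bilirubin row:** "ALT ≥ 3xULN and bilirubin ≥ 2xULN (>35% direct bilirubin"), so a raised total bilirubin counts only when more than 35% of it is direct.
- **Stopping table, other rows:** ALT ≥5×ULN; "ALT ≥ 3xULN persists for ≥4 weeks"; ALT ≥3×ULN with INR above 1.5 if measured; ALT ≥3×ULN when weekly monitoring is not possible; ALT ≥3×ULN with symptoms attributed to liver injury or hypersensitivity. Any of these stops the drug and carries the instruction "Report the event to GSK within 24 hours".
- **Footnote 1:** "If serum bilirubin fractionation is not immediately available, discontinue study intervention for that participant if" ALT is ≥3×ULN and bilirubin is ≥2×ULN.
- **Footnote 2:** a possible Hy's Law event "must be reported as an SAE (excluding studies of hepatic impairment or cirrhosis"). The bilirubin branch of that rule repeats the >35% direct condition.
- **Monitoring table:** ALT ≥3 but <5×ULN, with bilirubin below "2xULN, without symptoms believed to be related to liver injury or hypersensitivity and who can be monitored weekly for 4 weeks". The direct fraction is not mentioned. Treatment continues with weekly liver chemistry, and the first action is "Notify the GSK medical monitor within 24 hours of learning of the abnormality to discuss participant safety".
- **Step-down after four weeks:** if ALT is below 3×ULN and bilirubin is below "2xULN, monitor participants twice monthly until liver chemistries normalize or return to within baseline".

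**The concern.** The two tables appear meant to divide all ALT values of 3×ULN and above into those that stop the drug and those that are watched and notified. They do not meet. The stopping row leaves out raised bilirubin that is mainly indirect, and the monitoring row leaves out all bilirubin at or above 2×ULN, whatever its fraction.

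The result runs the wrong way. With ALT held fixed, a rise in bilirubin across 2×ULN removes a mandatory notification. Knowing that the direct fraction is ≤35% moves the participant from stopping (footnote 1) past monitoring to no Appendix 6 action.

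The pattern can be reached. Section 5.1 accepts isolated bilirubin above 1.5×ULN if it is fractionated with direct below 35%, or if the participant has Gilbert's syndrome, and gives no upper limit. Direct bilirubin is in the routine panel (Appendix 2, Table 11), so the fraction will normally be known. Section 2.3.1 names hepatic toxicity as a risk and cites Appendix 6 as mitigation. Section 2.2.1.1 reports raised liver enzymes and bilirubin in the rat, without giving the fraction.

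What is at stake is prompt sponsor awareness of a combined ALT and bilirubin rise.

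**Working it through.** The plan gives no figure to reproduce here, so the check is of the logic.

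**Side by side.** Take ALT 4×ULN, no relevant symptoms, INR 1.0, weekly monitoring possible, duration under four weeks.

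| Bilirubin (×ULN) | Direct fraction | Stopping table | Monitoring table | Appendix 6 action |
|---|---|---|---|---|
| 1.9 | 20% | not met | met | notify within 24 h |
| 2.0 | 20% | not met (≤35% direct) | not met (bilirubin not <2) | none |
| 2.0 | 40% | met | not met | stop, report within 24 h |
| 2.0 | not available | met (footnote 1) | not met | stop, report within 24 h |

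Appendix 6 has three automatic routes to the sponsor: the stopping-event report, the possible Hy's Law SAE and the monitoring-event notification. None applies in the second line.

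**Is this the only hole for this group?** The six stopping rows, footnote 1 and the monitoring row were coded and applied to every combination of:

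- 6 ALT values (3, 3.5, 4, 4.9, 5, 6×ULN)
- 6 bilirubin values (0.8, 1.5, 1.9, 2, 2.5, 4×ULN)
- 5 direct fractions (10, 34, 35, 36, 60%)
- 3 INR values (1.0, 1.5, 1.6)
- yes or no for symptoms, monitorability, four-week persistence and availability of fractionation

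This gives 6 × 6 × 5 × 3 × 2⁴ = 8,640 combinations. Exactly 72 meet neither table. All 72 have ALT 3 to <5×ULN (4 values), bilirubin ≥2×ULN (3), direct ≤35% (3) and INR ≤1.5 (2), with no symptoms, monitorable, not persistent and fractionated: 4 × 3 × 3 × 2 = 72. No other uncovered pattern appears.

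**Edges.** On an ALT grid in steps of 0.01×ULN, all 200 values from 3.00 to 4.99 are uncovered at bilirubin 2.0 with 20% direct, and at 2.5 with 20% or 35% direct. None is uncovered at bilirubin 1.99, or at 2.5 with 36% direct. The 200 describes the width of the interval. It is not a frequency.

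**Time to the first mandatory Appendix 6 action.** If the pattern continues without symptoms, the persistence row acts first. With visits every 7 days, that is 4 × 7 = 28 days after first detection. With the ±3-day window (Section 1.3, Table 2, footnote 3), the longest case is detection at shift −2, the fourth following visit at shift −3 (28 − 3 + 2 = 27 days, just short) and the fifth at shift +3 (35 + 3 + 2 = 40 days). The range is 28 to 40 days, against 1 day for the missing notification.

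**Effect of the fix.** Adding bilirubin ≥2×ULN with fractionated direct ≤35% to the monitoring row brings in all 72 combinations and leaves 0 of the 200 grid values uncovered. The added condition excludes direct >35% and unfractionated samples, so it does not overlap the bilirubin stopping row.

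**The case against.** **The exemption looks deliberate.** The >35% qualifier and the eligibility note both discount indirect hyperbilirubinaemia such as Gilbert's syndrome. That explains why this pattern does not stop the drug. It does not explain losing the notification, because the same ALT with normal bilirubin is notified.

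**Participants are not left unwatched.** A reader might infer that this pattern escapes follow-up. The documents do not support that. Chemistry is scheduled on Days 1, 8, 15 and 22 and then weekly (Section 1.3, Table 2), which matches the monitoring frequency. Section 8 sends immediate safety concerns to the sponsor, and Section 8.2.6 has clinically significant values repeated. Symptoms, INR above 1.5, inability to monitor and four-week persistence still stop treatment. This objection largely stands, although the Section 8 and 8.2.6 routes depend on the investigator's judgement and the 24-hour trigger does not.

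**Other rules may act first.** A reader might take 28 to 40 days as the delay before any mandatory protocol action. That is too strong, because the figure covers Appendix 6 only. Table 6 makes a Grade 3 laboratory abnormality lasting more than 3 days, or a Grade 4 one, a DLT criterion, subject to attribution and the 21-day window. The Grade 3 entry for other toxicities in Table 14 (Appendix 12) requires a hold and discussion with the medical monitor. Either might apply at higher bilirubin. The documents do not give the CTCAE bilirubin cut-offs, and Table 14 sends liver events back to Section 7.1.1, so this remains open. The laboratory listing for dose-escalation review (SAP Section 3.1.1.1) also shows Grade 2 and above values, but not within 24 hours.

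**Figure 3 may cover it.** Section 7.1.1 points to Figure 3, which is not shown in the available text. The finding is therefore limited to the tables.

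**Conclusion.** The gap in the Appendix 6 tables is real for the entry ALT ≤2.5×ULN group. It is a minor patient-safety wording correction. What is lost is an automatic 24-hour notification; testing continues.

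It rests on all of the following holding together: ALT 3 to <5×ULN, bilirubin ≥2×ULN, a known direct fraction ≤35%, no relevant symptoms (Appendix 6, footnote 3 counts fatigue, nausea, vomiting and jaundice when believed to be related to liver injury), INR ≤1.5 or not applicable, weekly monitoring possible, and less than four weeks' duration. The documents do not give the number affected. It is probably very small, and since SAP Section 2.1 states that enrolment has ended, only participants still on drug could be concerned.

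A reader might want to extend the point to the liver-metastasis rows of Appendix 6. Section 5.1 allows entry ALT above 2.5×ULN only in Part 2, and SAP Section 2.1 says Part 2 will not take place, so no edit is needed there.

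**What to change.** In the increased-monitoring criterion for entry ALT ≤2.5×ULN, replace the bilirubin condition by: *bilirubin <2×ULN, or bilirubin ≥2×ULN with fractionated direct bilirubin ≤35%*. Check that Figure 3 agrees.

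Leave the four-week step-down sentence unchanged. Matching words there would weaken a safeguard. At ALT 2.8×ULN and bilirubin 3.0×ULN with 20% direct, the current text refuses the move to twice-monthly checks because bilirubin is not below 2×ULN, and the matched text would allow it.

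The cost is one phrase in one table and a few extra notifications, for example for participants with Gilbert's syndrome. They remain on weekly checks that are already scheduled. No new test or visit is needed, and no stopping rule changes.
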